### **Order of Procedures**

At the beginning of the initial study visit, a study team member will first explain the nature of the study and obtain the volunteer's consent. The consent form will be explained and then it will be given to the participant to read. The participant will be encouraged to ask any questions he or she might have, and the team member will provide answers. After it is clear that the participant understands the nature of the study, the team member will emphasize that the participant is under no obligation to participate and will offer to answer questions about the study at any time during the participant's participation. If the participant agrees to participate in the study, he or she will be asked to sign the consent form, and a description of privacy information to be collected and how such information will be used (for Veterans, the HIPAA form will be used; for non-Veterans, the VA Notice of Privacy Practices form will be used). A copy of the consent form and relevant privacy form will be given to the participant along with a copy of the California Experimental Research Subject's Bill of Rights.

Next, the volunteer will undergo routine audiological screening (standard-of-care procedures) as described above to verify their hearing eligibility. If their audiological results are not appropriate for the study, they will be dismissed and will receive a payment of \$10/hour of participation as compensation for participating in this initial session, and our thanks. If the volunteer is suitable for the experiment, the experimental procedures will begin.

All participants will undergo otoscopy, immittance testing, TEOAE testing, word testing, and sentence testing at each visit. Participants in the experimental group will also complete the auditory training program, with baseline (pre-training) measures at visit 1, training occurring in visits 2-11, and visit 12 serving as the retention (post-training) measurements. These participants will therefore undergo a total of 15 hours of auditory training spread across 10 visits, plus pre- and post-tests. Pure-tone audiometry will be repeated for all participants at visits 6, 11, and 12 to detect any significant changes in hearing thresholds during the course of a participant's participation (not due to actual participation in the study because all sound levels will be presented at safe volumes). Such changes in audiometric measures are not likely to occur over this relatively short time period. All participants (except those in the Speech group) will be asked to return for a visit twice a week for the first 6 weeks (visits 1-11) and return for the final visit 4 weeks later (visit 12). Each subject will be allowed a maximum of two make-up visits in case a visit needs to be stopped early, resulting in a maximum of 14 study visits.

### **Personal Information to be Collected**

Individuals who make initial contact regarding the study will provide authorized study staff with their first and last name and last 4 of SSN. This information will be stored on the password-protected [REDACTED]. This information will be used to determine participant eligibility (via previous audiograms stored in CPRS, if any exist) and to schedule a study visit in VISTA if the individual is interested in participating. These individuals

will also answer several questions over the phone to study staff, which are related to the inclusion and exclusion criteria.

Personal information to be collected for participants participating in the research study will include first and last name, address, phone number, date of birth, full SSN, and hearing screening results conducted for the current study. This information is necessary to determine eligibility, contact the individual, document informed written consent, access medical records and write progress notes in CPRS, and to process the payment for participation.

This information will be stored on a password-protected document saved on [REDACTED], and only authorized lab members will have access. Participants will be assigned an experimental ID number in sequential order. This document will also serve as the linkage log that links participant names with ID numbers. The signed informed consent document will be stored in the locked filing cabinet, stored separately from any experimental data. In order for LLVARE to process participant payments, participants will fill out an IRS W9 form and a participant payment form. Both forms will contain the participant's first and last name, address, and full SSN. Copies of these forms will be stored in a locked filing cabinet in a locked office within the lab, stored separately from the experimental data. The original copies will be sent to the LLVARE business office via interoffice mail.

Participants expressing an interest in being contacted for future studies will indicate their agreement by initialing the designated part on the informed consent document. For these individuals, their first and last name, date of birth, last 4 of SSN, phone number, and hearing screening results will be saved on a password-protected file on [REDACTED] that will only be accessible to authorized study staff.

### **Risk to Participants**

This is a minimal risk study. The participants will all be healthy adults (other than mild hearing loss in some participants). There are no foreseeable risks involved in these studies beyond those associated with routine audiological practice, such as boredom or fatigue during testing. All sound levels to be used in the studies fall below the Damage Risk Criteria established by OSHA for intensity-duration interaction. If there is a breach of confidentiality, participants' personal information (name, address, date of birth, last 4 of SSN, and hearing ability) may be revealed.

### **Steps Taken to Minimize Risks and Data Safety Monitoring**

Participants will be provided with as many breaks during testing as they or the experimenter feel are helpful to minimize mental fatigue and boredom. Loudness levels of stimuli are carefully controlled, with frequent calibration and monitoring of laboratory equipment. Participant confidentiality will be protected by using only participant codes (three numbers) to label data collection sheets and computer data files. Participant numbers will be assigned sequentially and will not contain identifying information. Neither names nor social security numbers will be included in the participants' data files, although names and contact information will be filed separately so that participants can be contacted for future appointments. Signed consent forms will be stored separately from the experimental data as well. Any written or oral report or publication of the information obtained in this study will not contain the names of participants or identifying information. All data records will be stored on password-protected computers or as hard copy in locked offices or laboratories. Data are stored in the laboratory and/or in the experimenter's office, both of which are kept locked when no one is there.

Participant safety and comfort and data collection will be constantly monitored for each participant by the research team member collecting the data for that participant. Overall data collection will be monitored by the Principal Investigator, [name]. Following completion of the study, all data will be maintained in accordance with VHA guidelines.

### **Benefits of Participating**

All individuals will receive an up-to-date hearing screening and a further understanding of their own hearing. Participants in the Experimental group may or may not notice an improved ability to hear sounds in background noise after undergoing auditory training. The knowledge gained from this study may also benefit individuals with hearing-in-noise problems by contributing to improved diagnosis and treatment of hearing-in-noise problems in Veterans and in the civilian population.

### **Data Analysis**

Correlational analyses will be used to determine the correspondence between changes in MOC activity and changes in speech perception during the course of auditory training. Statistical analyses of test-retest reliability from the Control group data will be used to determine what constitutes a statistically significant change in MOC activity and speech perception ability. Repeated measures analyses of variance (both within a study visit and across study visits) will also be performed.

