## **Participant Groups**

Participants will be randomly assigned *a priori* to either the Experimental group (auditory training) or Control group (no auditory training) using simple random assignment. Because the third group (Speech Group) is added after the experimental and control groups have completed their participation, to provide additional power to the regression analysis, the Speech group will be assigned by the investigator. Because this study will detect whether or not significant changes in MOC activity and speech perception across time occurred as a result of auditory training, the Control group is needed to establish the test-retest reliability of our outcome measures in the absence of any training. Participants will be informed of which group they are assigned to at the initial visit, but they will not be allowed to change groups.

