### **Instrumentation**

Standard-of-care screenings and experimental testing will be carried out in a double-walled sound-isolated audiometric chamber adjoined to a single-walled room in the Auditory Research Laboratory, located at the VALLHS. Initial audiometric testing using standard-of-care procedures will be conducted to verify eligibility for the study and will be carried out using standard clinical equipment. A Grason-Stadler (GSI 61) clinical audiometer calibrated to standards (American National Standards Institute, 1996) will be used to deliver the pure-tone signals for threshold testing through Etymotic Research ER-3A insert earphones. Speech audiometry will be achieved by presenting words (pre-recorded or live voice) through insert earphones via the audiometer. A Grason-Stadler Tymptstar Middle Ear Analyzer acoustic-immittance meter will be used for immittance measurements to verify normal middle ear function. A visual inspection of participants' ear canals and tympanic membranes will be performed using a Welch-Allyn otoscope.

Experimental tests will consist of TEOAE testing, word/sentence recognition testing, and an auditory training program (only participants in the Experimental group will undergo the auditory training). For all experimental testing, participants will be seated in the sound booth. TEOAE testing uses an Etymotic Research ER-10D microphone and loudspeaker assembly. The hardware is controlled by a computer-based otoacoustic emissions system (Intelligent Hearing Systems) that interfaces with the MATLAB programming language. The software allows for the selection of sounds, as well as parameters of the testing such as duration, amplitude, and rate of stimulus presentation. For word and sentence testing, pre-recorded speech stimuli (saved as digital computer files) are presented through insert earphones using custom MATLAB software. Participants will make responses either by

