### Experimental Procedures

The following experimental procedures will be conducted:

TEOAE Testing: The basic task of the participants is similar to TEOAE procedures used clinically to evaluate hearing function objectively. Testing involves listening to sounds presented through earphones while seated comfortably in a sound-treated booth, and remaining alert but quiet in order to successfully measure responses from the cochlea and brainstem. Excessive body movement, swallowing, coughing, talking, and chewing creates acoustic and electric noise that can obscure recordings of TEOAEs, so it is imperative that participants remain as still as they can during the measurements. The experimental measurements differ from clinical measurements primarily in the types of sounds presented, the data analysis, and the use of an attention task to keep participants alert and awake. Specially constructed stimuli intended to stimulate the MOC system will be generated digitally on a computer, and played out to the listener using high-quality digital-to-analog converters, attenuators, filters, and other laboratory equipment. These sounds involve amplitude-modulated tones, click trains, and white noise. All stimuli will be presented at moderate volumes that are well below sound levels considered hazardous by OSHA and NIOSH standards. TEOAE measurements consist of waveforms, which are changes in sound amplitude across time. MOC function will be quantified as the change in waveform amplitude with versus without white noise presented to the opposite ear, where a larger change indicates stronger MOC activity. Repeated measurements will be obtained (both within a study visit and across study visits) to determine the change in MOC activity across time. Immittance audiometry will be obtained immediately prior to TEOAE testing at each visit to ensure that middle ear function is normal (successful measurement of TEOAEs requires normal middle ear function).

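### The correlation of MOC change with speech change is planned, as written, only for the trained group, with no Control estimate or between-group comparison, so it cannot show that the coupling is due to training.

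*Combined protocol and SAP*

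**What the plan says.** The first analysis named in Data Analysis is correlational: it is meant to "determine the correspondence between changes in MOC activity and changes in speech perception during the course of auditory training". Instrumentation states that "only participants in the Experimental group will undergo the auditory training", so as written this analysis covers that group alone.

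Control data have one stated analytic use. Participant Groups says "the Control group is needed to establish the test-retest reliability of our outcome measures in the absence of any training", and Data Analysis says "Statistical analyses of test-retest reliability from the Control group data will be used to determine what constitutes a statistically significant change" in MOC activity and in speech perception. The repeated-measures ANOVA sentence names no group factor and no group-by-time term.

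The data for a comparison would exist. Order of Procedures says "All participants will undergo otoscopy, immittance testing, TEOAE testing, word testing, and sentence testing at each visit", and the Experimental and Control groups follow the same 12-visit schedule. Participant Groups assigns these two groups at random.

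**The concern.** The Synopsis builds the study on an earlier report in young normal-hearing adults, where MOC strengthening in some trainees went along with their gains in hearing speech in noise. It asks whether this extends to older adults and those with mild hearing loss. The correlation of changes is the analysis that speaks most directly to that question, and a significant result would naturally be read as training acting on both.

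MOC activity and speech perception are measured at the same visits. A participant who is tired or inattentive at one visit may do poorly on both and then appear to improve on both. The protocol recognizes such states: TEOAE testing includes "the use of an attention task to keep participants alert and awake", and Risk to Participants lists effects "such as boredom or fatigue during testing". The reliability limits from Controls judge each outcome separately, so they do not remove non-training change that is correlated across the two. Without the Control correlation, the planned analysis has no reference for how much correlation arises untrained.

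**Working it through.** **Inputs.** From Sample Size: at least 12 Experimental participants, an equal number of Controls, up to 20 per group planned, type I error 0.05. Sidedness is not stated, so two-sided is assumed. Also assumed: one change score per participant for each outcome, and a non-training correlation rho of 0.2 to 0.4.

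**1. The plan's own figure.** The minimum sizes (10 for MOC, 12 for words, 11 for sentences) are for a paired difference in means at 80% power. The means and standard deviations behind them are not given, so they cannot be reproduced. Solved backwards with a two-sided paired t-test, they imply standardized differences of about 1.00, 0.89 and 0.94. None concerns a correlation. The smallest single-group correlation with 80% power is tanh((1.960 + 0.842)/sqrt(n − 3)):
- n = 12: tanh(2.802/3.000) = 0.73
- n = 20: tanh(2.802/4.123) = 0.59

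**2. Experimental-only test with no training coupling.** Let MOC change = S + e1 and speech change = S + e2, where S is a participant-specific shared state with variance rho and each e has variance 1 − rho. The true correlation is then rho. The test is t = r·sqrt((n − 2)/(1 − r²)) on n − 2 degrees of freedom. Over 40,000 simulated studies per row (simulation standard error at most 0.25 percentage points):

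| rho | n = 12 | n = 20 |
|---|---|---|
| 0 | 5.1% | 5.0% |
| 0.2 | 9.2% | 13.4% |
| 0.3 | 15.7% | 25.6% |
| 0.4 | 25.9% | 43.1% |

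**3. Between-group test in the same simulations.** With the same rho in Controls, z = (atanh r_E − atanh r_C)/sqrt(2/(n − 3)) rejects in 4.9% to 5.2% of studies in every row.

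**4. Drift identical in all participants.** With 12 participants, 12 visits, a linear drift of 0.5, 1.0 or 1.5 SD in both outcomes and 4,000 runs, the between-participant correlation of changes (last visit minus first) is significant in 5.7%, 5.3% and 4.6%, which is nominal. If visits are instead pooled after centring within participant, the rates are 6.4%, 19.6% and 61.8%. The plan does not say which kind of correlation it will use.

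**5. Precision of the comparison.** The standard error of the difference on the Fisher z scale is sqrt(2/(n − 3)).
- 20 per group: sqrt(2/17) = 0.343; half-width 1.96 × 0.343 = 0.67; power for r = 0.6 (atanh = 0.693) versus 0 is Φ(0.693/0.343 − 1.96) = Φ(0.06) = 52%.
- 12 per group: sqrt(2/9) = 0.471; half-width 0.92; power Φ(0.693/0.471 − 1.96) = Φ(−0.49) = 31%.

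These figures are for correlations. A slope comparison will be similarly imprecise, but not identical.

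**The case against.** **The plan is silent rather than exclusive.** Data Analysis is three sentences long and does not bar Controls from the correlation. Participant Groups also mentions a regression to which the Speech group adds power, so untrained participants enter some association analysis. This stands in part: a reader might infer that Controls are deliberately excluded, and the text does not say that. But the regression's outcome, predictors and groups are never defined, and the Speech group is assigned by the investigator after the other groups finish. It does not supply the missing comparison.

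**The change score is undefined.** A reader might take both changes to subtract the visit 1 values. Visit 1 is named as the Experimental baseline, but no section defines the change. A slope or average over many visits would dilute day-specific states. This stands, and it makes the rates in step 2 conditional.

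**There are safeguards.** The attention task, immittance checks before each TEOAE test, repeated thresholds and rest breaks all reduce the problem. MOC activity is itself a contrast with and without opposite-ear noise, which may cancel some state effects. These make a large rho less likely, but they do not show that it is zero.

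**Controls are not a perfect null.** Experimental participants also do 15 hours of training across visits 2 to 11, which may alter fatigue. A similar slope in both groups would not disprove training coupling either. Suppose each change has variance 1 and covariance 0.3 in Controls (slope 0.3), and training adds variance 1 to each and true covariance 0.3. The Experimental slope is (0.3 + 0.3)/(1 + 1) = 0.3, the same despite real coupling. This stands and limits what a null comparison can say.

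**Conclusion.** The gap is real. As written, the correlation covers trained participants only, and nothing in the document provides the Control reference needed to attribute it to training. If non-training correlation were 0.2 to 0.4, an Experimental-only test would be significant in about 9% to 26% of studies at 12 participants and 13% to 43% at 20, against a nominal 5%. That range is assumed, and the rates apply to one change score per participant.

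Three stronger readings are not supported. First, that any shared session effect biases the result: a practice gain or drift equal in everyone leaves a between-participant correlation at about 5%. The bias needs states that differ between participants, or pooled visits. Second, that a correlation found here would be spurious: the documents do not show how large the non-training part is. Third, that a similar Control slope would prove general co-variation: the example above shows otherwise.

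**What to change.** In Data Analysis:
- Define the change score for MOC activity and for each speech outcome (which visits, and how repeated measures are combined), with one value per participant. State that visits will not be pooled as if independent.
- In the randomized Experimental and Control participants, regress speech change on MOC change, group, and group × MOC change. Keep the Speech group out of this comparison.
- Report the slope and correlation with 95% confidence intervals in each group, and the difference with its 95% interval.
- Describe coupling as training-related only if the interval for the slope difference excludes zero in favour of the Experimental group. Otherwise report the Experimental correlation as an association whose training-specificity is not established, without concluding that it is general co-variation.

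This needs no new visits, tests or participants. The cost is a more cautious claim. With a Fisher z half-width of about 0.67 at 20 per group and 0.92 at 12, the difference is mainly an estimate, and even a strong true difference will often not meet the criterion.

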#### **Study Synopsis**

The goal of this study is to determine the impact of an auditory training program on the function of the inner ear and auditory brainstem. In normal-hearing individuals, the medial olivocochlear (MOC) branch of the auditory efferent system appears to aid with hearing signals in noise. A previous study in young normal-hearing adults found that auditory training strengthened the function of the MOC system in some participants in a way that coincided with their improvements in perceiving speech sounds in background noise (de Boer and Thornton, 2008, *J Neurosci*, 28:4929-4937). The MOC function measured at baseline also predicted the amount of success from the auditory training. Although these results are promising, it is not known if they generalize to populations that often have hearing-in-noise problems such as older and hearing-impaired adults.

This study will examine how an auditory training program impacts MOC activity in a group of older adults with normal hearing or mild hearing loss. This is a prospective study utilizing a repeated-measures design. Participants will participate in a computerized auditory training program taking place over a maximum of one year. Transient-evoked otoacoustic emissions (TEOAEs) will be used to measure the strength of MOC activity at each visit. Performance on untrained stimuli (words and sentences) will also be measured. A control group (no auditory training) will also be used to establish test-retest reliability for TEOAE measurements and performance on the word and sentence testing. A second “speech” control group will only participate in speech testing and the TEOAE testing. The results of this study may contribute to the improved diagnosis and treatment of hearing-in-noise problems in Veterans and in the civilian population.

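### No direct Experimental-versus-Control test is written, so the plan does not commit to testing whether change is due to auditory training

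*Combined protocol and SAP*

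**What the plan says.** Under Participant Groups, people are allocated "to either the Experimental group (auditory training) or Control group (no auditory training) using simple random assignment". The same section says the study will detect "whether or not significant changes in MOC activity and speech perception across time occurred as a result of auditory training". That is a causal aim, and the allocation is the right design for it.

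The role given to the Control group is narrower. Participant Groups says "the Control group is needed to establish the test-retest reliability of our outcome measures in the absence of any training". The Study Synopsis agrees: "A control group (no auditory training) will also be used to establish test-retest reliability for TEOAE measurements".

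Data Analysis has three sentences:

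- The first plans correlations between change in MOC activity and change in speech perception during training.
- The second reads, in part, "Statistical analyses of test-retest reliability from the Control group data will be used to determine what constitutes a statistically significant change".
- The third reads "Repeated measures analyses of variance (both within a study visit and across study visits) will also be performed".

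Sample Size gives 80% power at a type I error rate of 0.05 for a paired pre/post difference in the same participants. The minimum n is 10 for MOC activity, 12 for words and 11 for sentences, which gives at least 12 in the Experimental group and the same number in Control. Recruitment is up to 20 per group to allow for attrition.

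**The concern.** Under Order of Procedures, everyone has TEOAE, word and sentence testing at every visit, and the regular schedule has 12 visits. Scores may move through familiarity with the tests or through drift, whatever the effect of training. A pre/post comparison within the trained group cannot separate these sources. The contrast between the randomised groups removes whatever change is common to both, and the data for it are already collected.

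The Control criterion is an indirect use of the comparison group. It would come close to the randomised contrast only if it were centred on the Control mean change and allowed for the sampling error of that mean. The plan states neither. A criterion built on Control spread alone leaves a mean practice gain in the trained group's result. At stake is whether a positive result can be attributed to training, which is the question the study sets itself.

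**Working it through.** **1. What is and is not written.** The three planned analyses are an association between two change scores, a Control-based criterion of unstated form, and an ANOVA with within-visit and across-visit dimensions. No section states a group factor, a group-by-visit term or a between-group contrast.

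**2. The plan's own figure.** The minimum sizes of 10, 11 and 12 cannot be reproduced, because the pre/post means and SDs are not in the documents. The standardised change each size implies can be solved for. With a paired t-test (two-sided 0.05 assumed, since sidedness is not given), power is P(|T| > t₀.₉₇₅,ₙ₋₁), where T is noncentral t with n − 1 df and noncentrality d√n. Setting power to 0.80 gives d = 0.996 (n = 10, MOC), 0.938 (n = 11, sentences) and 0.889 (n = 12, words), in units of the SD of change.

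**3. False positives when only practice acts.** Assume a practice gain g of 0.3 or 0.5 SD of change, equal in both groups, and no training effect. The range is an assumption; the documents give no figure.

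| Procedure | n = 12, g = 0.3 / 0.5 | n = 20, g = 0.3 / 0.5 |
|---|---|---|
| Paired pre/post test, trained group (noncentrality g√n: 1.04 / 1.73 and 1.34 / 2.24) | 15.8% / 35.3% | 24.7% / 56.4% |
| Control-SD criterion on the trained mean, not centred (simulation) | 15.9% / 35.4% | 24.6% / 56.3% |
| Same, centred, Control mean treated as known | about 15% | about 15% |
| Two-sample test on change | 5% | 5% |

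The third row can be checked by hand. The difference between the two mean changes has variance 2σ²/n, but the criterion allows only σ²/n. The rejection rate is therefore 2·P(tₙ₋₁ > t₀.₉₇₅,ₙ₋₁/√2):

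- n = 12: 2.201/1.414 = 1.556, giving 14.8%.
- n = 20: 2.093/1.414 = 1.480, giving 15.5%.

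**4. Power of the missing contrast.** For a two-sample t-test on change with equal SDs, df = 2n − 2 and the noncentrality is (d − g)√(n/2), where g is now the change in Control. For example, with d = 0.889, g = 0 and n = 12, the noncentrality is 0.889 × √6 = 2.18 and power is 54.8%.

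| Implied d | Control change g | Power, 12 per group | Power, 20 per group | n per group for 80% |
|---|---|---|---|---|
| 0.996 | 0 | 64.5% | 86.6% | 17 |
| 0.938 | 0 | 59.3% | 82.4% | 19 |
| 0.889 | 0 | 54.8% | 78.2% | 21 |
| 0.996 | 0.3 | 37.1% | 57.3% | 34 |
| 0.938 | 0.3 | 32.1% | 50.2% | 40 |
| 0.889 | 0.3 | 28.1% | 44.2% | 47 |
| 0.996 | 0.5 | 21.3% | 33.3% | 65 |
| 0.938 | 0.5 | 17.7% | 27.1% | 83 |
| 0.889 | 0.5 | 14.9% | 22.4% | 105 |

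The smallest contrast detectable with 80% power is 1.20 SD of change at 12 per group and 0.91 SD at 20.

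**5. Baseline adjustment.** With equal variances and a baseline-to-follow-up correlation r, the standardised contrast is divided by √((1 + r)/2) and one df is lost. For r from 0.5 to 0.9 (assumed), power is 57% to 77% at 12 per group and 80% to 94% at 20 if Control does not change. With a shared gain of 0.3 to 0.5 SD it is 15% to 47% and 23% to 70%.

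**The case against.** The strongest reply is that the contrast is unstated rather than excluded. The ANOVA sentence does not rule out a group term. Data Analysis is also visibly incomplete, since Participant Groups mentions a regression analysis that it never describes. This is true, and the point here is limited to what the plan commits to. But leaving the key test optional leaves its choice open until the data are seen.

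Second, the Control criterion may be meant for individuals. On that reading an uncentred limit (t × Control SD) flags about 6% to 8% of untrained-effect participants under the same assumed gains, and a centred prediction limit flags 5%. Those figures are correct, but they are rates per participant. They do not answer whether the training group changed because of training.

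Third, Data Analysis does not name a paired pre/post test; that test appears only under Sample Size. The rates in the first row of the table therefore apply to an across-visit analysis of the trained group alone, or to an uncentred group-mean criterion. Both are open readings of the text.

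Fourth, the practice gain is assumed, and the same range is used for a physiological measure and for two behavioural ones. It may well differ between them. Finally, 20 per group is the recruitment ceiling, so the n = 20 figures assume no dropout. Both limits affect the sizes and not the omission.

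**Conclusion.** The concern holds. The plan randomises to answer a causal question but writes no comparison of the randomised groups, leaves the form of its indirect Control criterion undefined, and powers only a within-group change. This can credit a shared practice gain to training: with an assumed gain of 0.3 to 0.5 SD of change, the group-level false-positive rate could be anywhere from about 15% to 56%, depending on the procedure and group size, against a nominal 5%. The sizes rest on that assumed gain, on two-sided testing and on equal SDs of change in the two groups. The omission rests on the text alone. It should be corrected before any result is presented as an effect of training.

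**What to change.** In Data Analysis, state an Experimental-versus-Control contrast in all randomised participants for MOC activity, word recognition and sentence recognition. Adjust it for the visit-1 value, or use the group-by-visit term of the planned repeated-measures ANOVA, and report a 95% CI. Name one visit in advance; Order of Procedures already labels visit 12 as the retention (post-training) measurement. Say how participants without a value at that visit are handled.

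Leave the Speech group out of this contrast. It "is added after the experimental and control groups have completed their participation", and "the Speech group will be assigned by the investigator", so it is not part of the randomised comparison. Keep the Control test-retest band as a descriptive tool, centre it on the Control mean change, and say whether it applies to individuals or to group means.

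In Sample Size, say that the 80% power belongs to the paired pre/post test only, and give between-group power as a range like the one above. If the contrast is added after the data were seen, label it post hoc.

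The cost is lower stated power, not extra work: both groups already have the same outcome tests at each visit. With no Control change, 80% power needs 17 to 21 completers per group without adjustment. With a shared gain of 0.3 to 0.5 SD it needs 34 to 105, well beyond the planned 20. If recruitment to the two randomised groups has closed, those numbers serve to interpret a null result and not to set enrolment.
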